9.8.3 Outcome

The clinical outcome of the AE or SAE will be characterized as follows:

Death	The SAE CRF must be completed for this outcome
Recovered without sequelae	The patient returned to baseline status
Ongoing	Patient did not recover and symptoms continue;
Recovered with sequelae	The patient has recovered but with clinical sequelae from the event
Unknown	The patient outcome is unknown

9.8.4 Treatment or Action Taken

The treatment or action taken after the occurrence of an AE or SAE will be reported as:

Interventional Treatment	Surgical, percutaneous or other procedure
Medical Treatment	Medication dose reduction/interruption or discontinuation, or medication initiated for event
None	No action is taken

9.9 Reporting

9.9.1 General Adverse Event Reporting Procedures

Investigators are required to keep records on “all relevant observations, including records concerning adverse device effects (whether anticipated or unanticipated)” according to 21 CFR 812.140. Adverse event collection will occur from the point of study enrollment to study closure. All new or worsening (from baseline) clinically significant adverse events will be captured on the AE CRF through the 90-day follow-up telephone visit. Non-clinically-significant adverse events will not be required post discharge from the initial study procedure. It is the responsibility of the Investigator to assess the subject for adverse events and, if it is determined that a clinically significant AE has occurred, to capture the required adverse event information on the AE CRF. Independent monitoring will be conducted (§14.1) to review source documentation and verify the complete and accurate capturing of adverse events.

The general procedure for investigators reporting any adverse event is as follows:

- If an adverse event occurs, complete all sections of the Adverse Event CRF
- Each unique event/diagnosis must be documented separately
- Documented pre-existing conditions are not considered to be reportable AEs unless there is a change in the nature or severity of the condition
- The AE CRF must be reviewed by the investigator

For adverse events not meeting the criteria for an SAE or (potential) UADE, the sponsor recommends that the Investigator notify the sponsor within 10 working days of first learning of the AE using the electronic data capture (EDC) CRF. If necessary, the Investigator may be requested to provide de-identified copies of source documentation (e.g., physician/nurse notes or summaries) regarding the event.

The Investigator must also notify the responsible IRB/EC regarding new and significant safety information and any events identified by Keystone Heart Ltd. that require expedited FDA or other regulatory authority reporting as serious, unexpected, and related to the investigational device. It is the responsibility of the investigator to ensure site-specific IRB/EC reporting requirement are met.

The sponsor is responsible for reporting SAEs and device deficiencies to regulatory authorities in line with applicable regulatory requirements and for reviewing the risk analysis, determining the need for corrective or preventative action, and informing investigators and regulatory authorities accordingly.

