Note: Enrollment in Phase I has been halted after enrolling a total of 258 subjects (54 roll-ins and 204 randomized subjects including 63 controls) based on a recommendation of the DSMB following interim data review at the prespecified interim analysis timepoint. A new generation device designed for increased efficacy, ease of use, and improved safety which will be tested in Phase II (below).

Phase II

In Phase II, up to 295 randomized subjects and 40-50 roll-in subjects will be enrolled at up to 25 sites in the United States (inclusive of sites enrolling subjects in Phase I). No single site will be permitted to enroll more than 20% of all randomized subjects in Phase II.

Subjects with indications for TAVI and who meet study eligibility criteria will be randomized 2:1 (stratified by study site) to one of two treatment arms:

- **Intervention** – TAVI with the TriGUARD 3 CEPD
- **Control** – standard unprotected TAVI.

Randomization will be stratified by implanted valve type (Medtronic vs. Edwards).

No single valve type will be implanted in more than approximately 70% of randomized patients (phase II).

Roll-in subjects (a minimum of 2 and a maximum of 3 Roll-ins per-site) will not be randomized, but will undergo TAVI with the TriGUARD 3 device. These cases will be proctored by a Sponsor representative.

All subjects will be followed clinically in-hospital and at 30 days, undergo diffusion-weighted MR imaging 2 to 5 days post-procedure, and undergo neurologic (NIHSS) testing pre-procedure, post-procedure (2-5 days post-procedure), and at 30 days. A follow-up phone-call to assess the occurrence of death or stroke will be done at 90 days.

The initial randomized cohort will consist of up to 225 subjects. After at least 50% of the initial randomized cohort (approximately 112 subjects) have reached the 30 day primary efficacy endpoint evaluation time point, a sample size re-estimation will be performed in case the conditional power of the trial (assessed by the independent biostatistician) is >40% but <80%, subject to approval by the Sponsor. If this analysis determines that more than 225 randomized subjects will be required to ensure adequate study power, enrollment may continue until the required number of subjects have been enrolled, or until the total subject limit for the study has been reached (whichever occurs first).

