12-lead ECG ³	X		X		
Concomitant Medications	X	X	X	X	
Pregnancy Test ⁴	X				
Hematology/Chemistry ⁵	X		X		
Cardiac Enzymes ⁶	X ⁶		X ⁶		
CT Imaging ⁷	X				
Cerebral DW-MRI ⁸			X		
NIH Stroke Scale ⁹	X		X	X	
Modified Rankin Scale ⁹	X		X	X	
TAVI		X			
Echocardiography (SOC) ¹⁰			X		
Device deployment		X			
Adverse Events		X	X	X	
Phone call to assess mortality/ Stroke					X

¹ Physical examination to include heart rate, blood pressure, and ischemic/anginal status (CCS or silent ischemia). The screening/baseline assessment must also include NYHA functional capacity, height, and weight.

² If the full screening/baseline review of eligibility criteria is conducted before the day of enrollment, the following repeat review of selected eligibility criteria should be performed on the day of enrollment and randomization (§6.2.1) to confirm study eligibility, using the most recent available laboratory values and clinical assessments: 1) Ensure that the subject has not had symptoms or chemistry results indicating acute myocardial infarction (§6.1.2.1.5); 2) Ensure that the most recent eGFR remains ≥ 30 (§6.1.2.1.10); 3) Ensure that there are no signs of cardiogenic shock (§6.1.2.1.13); and 4) Review the planned approach for TAVI, as certain approaches will make the subject ineligible for the study (§6.1.2.1.1).

³ Screening/baseline ECG may be performed up to 30 days prior to procedure, as long as there have been no intervening signs or symptoms of myocardial ischemia (in which case the ECG should be performed within 24 hours prior to enrollment). The post-procedure ECG must be performed within 24 hours of the procedure or prior to hospital discharge (whichever occurs first).

⁴ Female patients of childbearing potential must have a pregnancy test within 14 days prior to the procedure

⁵ Hematology and chemistry within 14 days prior to the procedure are defined in §7.2.

⁶ For the screening/baseline assessment, cardiac enzymes (CK), isoenzymes CK-MB or troponins obtained up to 14 days prior to the procedure (or on current admission) are acceptable, provided there has been no intervening episode of myocardial ischemia (in which case cardiac enzymes should be confirmed within 24 hours prior to enrollment). Post-procedure CK/CKMB or troponin (preferably CKMB isoenzyme) will be measured post procedure when clinically indicated. If cardiac biomarkers are elevated, they should be repeated per local standard of care.

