7.7 Three-month Follow-up

7.7.1 Phase I:

All subjects in Phase I were expected to return to the clinic at 90 days (\pm 14 days) post-procedure for a clinical evaluation.

The 90 day follow-up visit consisted of the following assessments:

- Physical examination including ischemic / anginal status (CCS or silent ischemia), heart rate, and blood pressure
- Frailty assessment with the Clinical Frailty Scale
- Documentation of any adverse events/ serious adverse events occurring since the previous evaluation
- Current concomitant medication documentation, including antiplatelet and anticoagulant therapy
- NIH Stroke Scale (NIHSS): Neurologic status evaluation using the NIH stroke scale must be performed by a neurologist or a clinical designee (e.g. neurology fellow).
- Modified Rankin Scale (mRS) must be performed by a neurologist or a clinical designee (e.g. neurology fellow).
- A full neurological evaluation should be performed by a neurologist in all patients in whom a stroke or TIA is suspected on the basis of the NIHSS, mRS, or other signs or symptoms.
- A neuropsychological test battery (§16.7), to be administered by a qualified individual. The test battery includes:
 - Montreal Cognitive Assessment (MoCA)
 - Repeatable Battery for the Assessment of Neuropsychological Status (RBANS)
 - Trail Making Test Parts A and B

- The Short Form 36 Health Survey (SF-36)

Note: All clinically significant adverse events should be carefully documented by the research staff using the adverse event data forms. Any clinically-indicated neuroimaging should be forwarded to the MRI Core Laboratory.

7.7.2 Phase II:

In Phase II, a telephone contact at 90 days (\pm 14 days) post-procedure will establish:

- Mortality
- Stroke

If death or stroke is reported, source documentation will be requested from treating facility to enable CEC adjudication of cause of death (cardiovascular [subclassified and neurologic-event related] or non-cardiovascular) and stroke classification according to the protocol-specified definitions.

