8.0 Device Accountability

The Site Principal Investigator is responsible for device accountability at his/her trial site and must maintain associated trial records according to 21 CFR Part 812.140 (§15.5.2). The investigator may assign the responsibility for device accountability to an appropriate study staff member, but remains the final responsible person.

The investigator will maintain device use/disposition records that document device delivery to the trial site, the inventory at the site, administration to each patient as well as any device that was opened but not used. These records must include dates, quantities, batch/serial numbers, expiration dates, and the unique code numbers assigned to the trial patients. The investigator must maintain records that adequately document which device was used (or exposed to the circulation) of each subject and any device malfunctions.

At the trial closeout visit, the Investigator must return to the Sponsor any unused devices and a copy of the completed device inventory. The Investigator's copy of the device reconciliation records must document all device usage (including devices that were opened but not used) and any unused devices that have been returned to the sponsor.

9.0 Adverse Events, Serious Adverse Events, and End-points Potentially Meeting End-point Criteria

In this study, patients should be encouraged to report adverse events (AEs) spontaneously or in response to general, non-directed questioning. Any time during the study, the patient may volunteer information that resembles an adverse event (AE). If it is determined that a clinically significant AE has occurred, the investigator should obtain all the information required to complete the AE CRFs. Non-clinically-significant adverse events will not be required post discharge from the initial study procedure.

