12.4.9 Additional Analyses

The following data will be summarized using descriptive statistics presented by treatment group:

- Subject enrollment and data compliance by site and visit (data compliance at each visit is percent of patients whose data forms have been collected and entered divided by the percent of patients whose forms should have been collected and entered) (ITT, eITT, PT, and AT populations)
- Frequency (number and percent of patients) with each type of concomitant medication (AT population)
- Frequency (number and percent of patients) with each site-reported Treatment Emergent AE overall and by MedDRA system organ class and preferred term (a treatment emergent AE is an AE that started or worsened during or after the index procedure) (AT population)
- Frequency (number and percent of patients) with each site-reported Treatment Emergent Serious AE overall and by MedDRA system organ class and preferred term (AT population)
- Frequency (number and percent of patients) with each site-reported Treatment Emergent AE or SAE, by CEC-adjudicated relationship to the investigational device or procedure (AT population)
- Protocol deviations (number and percentage of patients with each deviation type) (ITT population)
- Kaplan-Meier plots for MACCE and TAVI early safety through 30 days (AT Population; patients without an event will be censored at 30 days or day of withdrawal, whichever is earlier)
- Detailed listings on primary and secondary endpoints, site-reported AE as well as protocol deviations

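### The 90-day adverse-event rule conflicts with the Phase II schedule, and the AE/SAE tables have no onset window or phase split, so comparisons across phases would rest on unequal scheduled observation

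*Combined protocol and SAP*

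**What the plan says.** **Collection rule.** Section 9.9.1 sets an open window, "Adverse event collection will occur from the point of study enrollment to study closure", and then a specific one: "All new or worsening (from baseline) clinically significant adverse events will be captured on the AE CRF through the 90-day follow-up telephone visit". Section 9.0 also allows passive reporting throughout: "patients should be encouraged to report adverse events (AEs) spontaneously or in response to general, non-directed questioning".

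**Phase II contact after day 30.** In Table 7a (section 7.1) the Adverse Events row is marked at the procedure, post-procedure and 30 days, and is blank at 90 days. The 90-day contact has its own row, "Phone call to assess mortality/ Stroke". Section 5.2 agrees: "A follow-up phone-call to assess the occurrence of death or stroke will be done at 90 days". Section 7.7.2 lists mortality and stroke as what the call establishes, and supporting records are sought only for those: "If death or stroke is reported, source documentation will be requested from treating facility".

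**Phase I contact after day 30.** Table 7 marks Adverse Events at 90 days. Section 7.7.1 describes a clinic visit that included "Documentation of any adverse events/ serious adverse events occurring since the previous evaluation".

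**Tables.** Section 12.4.9 plans, by treatment group in the As Treated population, "Frequency (number and percent of patients) with each site-reported Treatment Emergent AE overall and by MedDRA system organ class", and the same for serious AEs. Treatment-emergent is defined by a start (during or after the index procedure) and no end. The section does not split by phase or say which controls form the control column.

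**The concern.** Two things are wrong in the current text.

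First, a site that follows Table 7a and section 7.7.2 will not do what section 9.9.1 requires. The 9.9.1 wording cannot be a Phase I remnant, because the Phase I 90-day contact was a clinic visit and only Phase II has a telephone visit.

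Second, a percentage of patients with at least one event can only rise with longer observation. The AE/SAE tables set no onset limit, while Phase I subjects had a scheduled full AE review at 90 days and Phase II subjects had none. If columns from the two phases stand side by side, or are merged, part of any difference reflects the schedule. The event types exposed are those other than death and stroke, which are sought to 90 days in both phases.

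At stake is the descriptive AE profile of TriGUARD 3. Section 4.3.4 says the redesign is expected to improve safety over TriGuard HDH, so readers will look at exactly that pair of columns.

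**Working it through.** **1. Passages side by side**

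| | Phase I | Phase II |
|---|---|---|
| 90-day contact | Clinic visit (7.7.1) | Telephone call (7.7.2) |
| AE row at 90 days | Marked (Table 7) | Blank (Table 7a) |
| Asked at 90 days | All AEs and SAEs | Mortality and stroke |
| Last scheduled full AE review | Day 90 | Day 30 |
| AE/SAE table window (12.4.9) | None stated | None stated |

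The contradiction with section 9.9.1 follows directly. No arithmetic is needed for it.

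**2. Inputs for the size**

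- Phase I: 204 randomized, 63 of them controls (section 5.2), so 204 − 63 = 141 TriGuard HDH.
- Phase II initial cohort: 150 TriGUARD 3 and 75 controls (section 12.2.4.1.2).
- The plan's pooled control total reproduces: 63 + 75 = 138.
- Nominal days are used. The visit windows (±7 and ±14 days) are ignored.

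**3. Scheduled AE observation**

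- TriGUARD 3 v its concurrent controls: 30 v 30 days.
- TriGUARD 3 v TriGuard HDH: 30 v 90 days.
- TriGUARD 3 v 138 pooled controls: the controls' mean is (63 × 90 + 75 × 30)/138 = 7,920/138 = 57.4 days, and 57.4/30 = 1.91. The share of controls with a scheduled 90-day AE review is 63/138 = 45.7%, against 0% of TriGUARD 3 subjects.
- If Phase II reaches 295 randomized, it has about 98 controls. The share becomes 63/161 = 39.1% and the mean (63 × 90 + 98 × 30)/161 = 53.5 days.

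**4. What that could do to a percentage**

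The documents give no AE rates, so these are assumptions:

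- True risk is equal in all arms.
- p30, the proportion with an AE by day 30, is 25%, 50% or 75%.
- q, the proportion of the rest with a first AE between day 30 and day 90, is 5% to 30%.
- Nothing is captured after day 30 in Phase II.

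Gap against HDH = (1 − p30) × q. Gap against pooled controls = (63/138) × (1 − p30) × q.

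| p30 | HDH minus TriGUARD 3 (points) | 138 pooled controls minus TriGUARD 3 (points) |
|---|---|---|
| 25% | 3.75 to 22.5 | 1.7 to 10.3 |
| 50% | 2.5 to 15.0 | 1.1 to 6.8 |
| 75% | 1.25 to 7.5 | 0.6 to 3.4 |

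For example, at p30 = 50% and q = 30%: 0.457 × 0.50 × 0.30 = 6.8 points. Against concurrent Phase II controls the gap from the schedule is 0 points. With a common 30-day onset window it is 0 points in every comparison.

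**The case against.** The strongest reply is that no bias is demonstrated. TriGUARD 3 and its concurrent controls follow one schedule. The rule that lets poolability decide the control set is stated only for the primary efficacy endpoint (section 12.4.3 and the synopsis). Primary safety is reported separately for each phase (section 12.2.1.1.1), and performance endpoints and other measures are reported separately for each device (sections 5.4.2.1.7 and 5.4.3). Collection after day 30 is also not nil in Phase II: section 9.9.1 runs to study closure, section 9.0 accepts volunteered events, and sections 9.9.2 and 9.9.3 tie reporting to when the investigator learns of the event. Sections 5.1.1, 12.1 and 12.4.3 defer detail to an SAP, which might set the window. The tables are descriptive.

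Much of this stands. A reader might infer that AE percentages by arm generally favour TriGUARD 3. The documents do not support that: the randomized Phase II comparison is balanced, and section 12.4.9 does not place Phase I controls in the control column. A reader might also take section 12.4.9 to claim 90-day coverage, but it states no window at all. Passive reporting means that 30 v 90 and 30 v 57.4 days are upper bounds on the contrast.

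The reply does not close the gap. Section 12.4.9 does not exclude Phase I controls either. The As Treated definition (section 12.3.3) names both devices and a single control group. Section 5.1.1 speaks of using Phase I control data in evaluating the safety as well as the effectiveness of TriGUARD 3. Elsewhere the plan writes a phase split when it wants one (sections 12.4.2 and 12.4.3), and within section 12.4.9 it limits the Kaplan-Meier plots to 30 days. The AE/SAE tables have neither limit.

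**Conclusion.** The contradiction between section 9.9.1 and the Phase II schedule and call content is certain. So is the absence of an onset window and a phase split for the AE/SAE tables in section 12.4.9.

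The effect on comparisons is conditional. It arises when TriGUARD 3 is read beside TriGuard HDH, or if the control column includes Phase I controls, and it would then tend to favour TriGUARD 3. It does not arise against concurrent Phase II controls, where the AE record is incomplete after day 30 but equally so in both arms.

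The size is unknown. Under the stated assumptions it runs from 0.6 to 10.3 points against 138 pooled controls and from 1.25 to 22.5 points against HDH. These figures take late Phase II capture as nil, so passive reporting would shrink them.

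No formal conclusion depends on these tables. The primary safety test is a 30-day comparison with a fixed performance goal. The secondary safety endpoints are evaluated in hospital and at 30 days, with 90-day evaluation limited to mortality, stroke and overt CNS injury items.

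**What to change.** - **Section 9.9.1, Table 7a and section 7.7.2:** reconcile them so that the stated AE capture in Phase II matches what sites are scheduled to do. Keep the duty to report later events that become known. The analysis problem does not require ending AE capture at day 30, which would reduce safety collection for an investigational device.
- **Section 12.4.9:** limit the comparative AE and SAE tables to onset within 30 days of the procedure in both phases, the longest period with scheduled full AE review common to both.
- **Control column:** show controls by phase.
- **After day 30:** report 90-day death and stroke separately, since both phases seek them. List AEs with onset after day 30 by phase.

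The cost is wording and one date filter. The downside is that later AEs appear in a listing and not in the comparative tables.

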9.9.2 Serious Adverse Events

Keystone Heart Ltd. recommends that the Investigator notify the sponsor within 3 working days of first learning of any SAE using the EDC CRF. All cardiovascular events and all adverse events potentially meeting endpoint criteria will be considered an SAE (even if they do not result in death or prolong the hospitalization) and should be reported as well (see also section 11.2). If necessary, the Investigator may be requested to provide copies of de-

identified source documentation (e.g., physician/nurse notes or summaries) regarding the event. The sponsor will conduct an evaluation of the event and, if it is determined by the sponsor to be a UADE, it will be reported as described in the following section.

At EU sites (phase I), Serious Adverse Device Effects (SADEs) must be reported to genae, N.V. within 48 hours of knowledge if required by local or national regulations. Contact details are as follows:

genae, N.V.
[name]
[name]
[contact]
[contact]

It is the responsibility of each Investigator to report all serious adverse events and/or serious adverse device effects and device deficiencies that could have led to a serious adverse device effect to the IRB/EC, according to national regulations and IRB/EC requirements. If required by national regulations, the Investigator may also be required to report SAEs to the regulatory authority.

European investigators (phase I) who become aware of an event must report the event to **genae** and to the **Sponsor**. While there is no legal requirement within the Medical Device Directives obliging users to have an active role in the medical devices vigilance system, user involvement is critical to successful post market surveillance by 1.) Ensuring that suspected incidents are communicated to manufacturers, and 2.) Making the proper implementation of field safety corrective actions possible.

